2.6 Interim Analysis

No interim analysis is planned.

 GALDERMA	Title SAP, 43CH1508, Restylane Defyne NLF	Doc id MA-31549
---	--	--------------------

2.7 Determination of Sample Size

CCI

2.8 Changes in the Analysis Planned in the Protocol

Regarding statistical analysis in general (CSP Section 10.1), no *p*-values will be presented since no actual statistical testing will be performed.

In SAP Section 2.3, a list of protocol deviations disqualifying subjects from PP has been added.

Summaries of demographics and baseline characteristics (CSP Section 10.3) will not be summarized by study product since the same subject will be treated with both products.

CCI

Safety analysis of AEs (CSP Section 10.5) has been clarified.

 GALDERMA	Title SAP, 43CH1508, Restylane Defyne NLF	Doc id MA-31549
--	--	----------------------------------

3 Reference List

 GALDERMA	Title SAP, 43CH1508, Restylane Defyne NLF	Doc id MA-31549
---	--	--------------------

4 Appendix A: Study Subjects

4.1 Analysis Populations

Table 4-1: Analysis populations

Site	Subject number	FAS		PP		Safety	
		n	%	n	%	n	%
Site 1	1xx-1xx						
Site 2	2xx-2xx						
Site 3	3xx-3xx						
Site 4	4xx-4xx						
Total (N)							

% = $n/N * 100$

4.2 Protocol Deviations

Table 4-2: Protocol deviations affecting PP population

Protocol deviation	Subject number	Visit

Table 4-3: Protocol deviations not affecting PP population

Protocol deviation	Subject number	Visit

 GALDERMA	Title SAP, 43CH1508, Restylane Defyne NLF	Doc id MA-31549
---	--	--------------------

4.3 Disposition of subjects

Table 4-4: Disposition of subjects: screened, treated, completed, and withdrawn subjects by site

Site	Screened subjects		Treated subjects		Completed subjects		Withdrawn subjects	
	n	%	n	%	n	%	n	%
Site 1								
Site 2								
Site 3								
Site 4								
Total (N)								

$\% = n/N*100$

Table 4-5: Subject accountability by visit

Visit	Expected subjects	Screening failures	Treated subjects	WSRS performed	Completed subjects	Withdrawn subjects
	n	n	n	n	n	n
Screening						
Baseline (Initial treatment)						
Week 4 follow-up / Optional touch-up treatment						
Week 4 follow-up after touch-up treatment						
Month 3 after last treatment						
Month 6 after last treatment						
Month 9 after last treatment						
Month 12 after last treatment						

$\% = n/N*100$

 GALDERMA	Title SAP, 43CH1508, Restylane Defyne NLF	Doc id MA-31549
--	--	--------------------

Table 4-6: Summary of screening failures

Site	Subject screening number	Date of screening	Reason for screening failure

Any extra comments here ...

[figure not shown]
Table 4-7: Withdrawn subjects

Site	Subject number	Date of treatment		Last visit performed	Date of withdrawal	Reason for withdrawal
		Initial treatment	Optional touch-up treatment			

Any extra comments here ...

 GALDERMA	Title SAP, 43CH1508, Restylane Defyne NLF	Doc id MA-31549
---	--	--------------------

Figure 4-1: Flowchart of study visits and subject accountability

 GALDERMA	Title SAP, 43CH1508, Restylane Defyne NLF	Doc id MA-31549
---	--	--------------------

5 Appendix B: Demographics

5.1 Demographics and Baseline characteristics

Table 5-1: Summary of demographics and Baseline characteristics, all subjects

Treated subjects: N = xxx	
Characteristics	Result
Age (years)	
n	
Mean	
SD	
Minimum	
Median	
Maximum	
n (%)	
Gender	
Female	
Male	
Ethnic origin	
Han Chinese	
Other ¹⁾	
Baseline WSRS score	
Score 3	
Score 4	

% = $n/N \times 100$

1) Specification of Other: ..., ...,

Effective date: 2017-02-13 08:27

Effective

Version: 1.0

Treated subjects: N = xxx	
Vital signs	Result
Pulse rate (beats/min)	
n	
Mean	
SD	
Minimum	
Median	
Maximum	
Blood pressure (Systolic mmHG / Diastolic mmHG)	
n	
Mean	
SD	
Minimum	
Median	
Maximum	
Respiratory rate (breaths/min)	
n	
Mean	
SD	
Minimum	
Median	
Maximum	
Temperature (Axillary) (°C)	
n	
Mean	
SD	
Minimum	
Median	
Maximum	

 GALDERMA	Title SAP, 43CH1508, Restylane Defyne NLF	Doc id MA-31549
---	--	--------------------

5.2 Pre-treatment procedures

Table 5-2: Pre-treatment procedures by treatment visit, FAS

Procedure	Initial treatment Subjects: N = xxx	Optional touch-up treatment Subjects: N = xxx
	n (%)	n (%)
Urine pregnancy test¹⁾		
Negative		
Positive		
Pre-treatment photography²⁾		
No		
Yes		

$\% = n/N * 100$

1) If urine pregnancy test wasn't done for some subjects, note the subject number and treatment here.

2) If pre-treatment photography wasn't done for some subjects, note the subject number and treatment here.

 GALDERMA	Title SAP, 43CH1508, Restylane Defyne NLF	Doc id MA-31549
---	--	--------------------

5.3 Medical history

Table 5-3: Subjects reporting medical history/concurrent disease (relevant or major illness), FAS

Any medical history / concurrent disease	No		Yes		Total (N)	
	n	%	n	%	n	%

% = $n/N * 100$

Table 5-4: Subjects reporting medical history/concurrent disease (relevant or major illness) and number of events by MedDRA System Organ Class (SOC), FAS

Primary SOC	All			Ongoing at study start		
	Events		Subjects	Events		Subjects
	n	%	n	n	%	
Total¹⁾						

% = $n / \text{number of subjects in FAS (N = xxx)} * 100$

1) A single subject may have reported medical history (relevant or major illness) by more than one primary SOC category.

Table 5-5: Subjects reporting previous cosmetic/aesthetic procedures or implants, FAS

Any previous cosmetic/aesthetic procedures or implants	No		Yes		Total (N)	
	n	%	n	%	n	%

% = $n/N * 100$

Table 5-6: All previous cosmetic/aesthetic procedures or implants by procedure/product name and procedure/product location, FAS

Procedure/Product name	Procedure/Product location	Subjects	
		n	%

% = $n / \text{number of subjects in FAS (N = xxx)} * 100$

 GALDERMA	Title SAP, 43CH1508, Restylane Defyne NLF	Doc id MA-31549
---	--	--------------------

6 Appendix C: Concomitant medication and procedures / treatments

6.1 Concomitant medication

Table 6-1: Subjects reporting concomitant medication, FAS

Concomitant medication	Any concomitant medication?					
	No		Yes		Total (N)	
	n	%	n	%	n	%
Ongoing at study start						
Initiated during study						
Total						

% = $n/N * 100$

Table 6-2: Subjects reporting concomitant medication and number of medications by reason, FAS

Reason for concomitant medication	Subjects		Medications	
			All	Ongoing at study end
	n	%	n	n
Adverse Event				
Medical History				
Other				
Total¹⁾				

% = $n / \text{number of subjects in FAS (N = xxx)} * 100$

1) A single subject may have reported concomitant medication for several reasons.

 GALDERMA	Title SAP, 43CH1508, Restylane Defyne NLF	Doc id MA-31549
---	--	--------------------

Table 6-3: Subjects reporting concomitant medication ongoing at study start and number of medications by ATC code, FAS

ATC code	ATC text	Subjects		Medications
		n	%	n
Total¹⁾				

% = n / number of subjects in FAS (N = xxx) * 100

1) A single subject may have reported several types of concomitant medication.

Table 6-4: Subjects reporting concomitant medication initiated during study and number of medications by ATC code, FAS

ATC code	ATC text	Subjects		Medications
		n	%	n
Total¹⁾				

% = n / number of subjects in FAS (N = xxx) * 100

1) A single subject may have reported several types of concomitant medication.

Table 6-5: Subjects reporting concomitant medication taken due to an AE and number of medications, AE by MedDRA Preferred Term (PT) and relatedness, by ATC code, FAS

ATC code	ATC text	Concomitant medication		Adverse Event	
		Subjects	Medications	PT	Related AE
		n	n		
Total¹⁾					

% = n / number of subjects in FAS (N = xxx) * 100

1) A single subject may have reported several types of concomitant medication.

 GALDERMA	Title SAP, 43CH1508, Restylane Defyne NLF	Doc id MA-31549
---	--	--------------------

6.2 Concomitant procedures/treatments

Table 6-6: Subjects reporting concomitant procedures/treatments, FAS

Any concomitant procedures/treatments	No		Yes		Total (N)	
	n	%	n	%	n	%

% = $n/N * 100$

Table 6-7: Subjects reporting concomitant procedures/treatments and number of procedures/treatments by reason, FAS

Reason for concomitant procedure/treatment	Subjects		Procedures/treatments
	n	%	n
Adverse Event			
Medical History			
Other			
Total¹⁾			

% = $n / \text{number of subjects in FAS (N = xxx)} * 100$

1) A single subject may have reported procedures/treatments for several reasons.

 GALDERMA	Title SAP, 43CH1508, Restylane Defyne NLF	Doc id MA-31549
---	--	--------------------

7 Appendix D: Treatment procedure

Table 7-1: Volume (mL) injected per subject by treatment visit and treatment, FAS

Treatment visit	Restylane Defyne						Restylane					
	n	Mean	SD	Min	Median	Max	n	Mean	SD	Min	Median	Max
Initial treatment												
Optional touch-up treatment												
Total												

Table 7-2: Difference within subject (Restylane - Restylane Defyne) of injected volume (mL) by treatment visit, FAS

Treatment visit	Difference within subject					
	n	Mean	SD	Min	Median	Max
Initial treatment						
Optional touch-up treatment						
Total						

Table 7-3: Injection time (minutes) at initial treatment by treatment, FAS

Treatment visit	Initial treatment					
	n	Mean	SD	Min	Median	Max
Restylane Defyne						
Restylane						
Difference within subject (Restylane - Restylane Defyne)						

 GALDERMA	Title SAP, 43CH1508, Restylane Defyne NLF	Doc id MA-31549
---	--	--------------------

Table 7-4: Volume (mL) injected per subject by site, treatment visit and treatment, FAS

Site	Restylane Defyne						Restylane					
	n	Mean	SD	Min	Median	Max	n	Mean	SD	Min	Median	Max
Volume (mL) injected at initial treatment												
Site 1												
Site 2												
Site 3												
Site 4												
Total												
Volume (mL) injected at optional touch-up treatment												
Site 1												
Site 2												
Site 3												
Site 4												
Total												
Total volume (mL) injected												
Site 1												
Site 2												
Site 3												
Site 4												
Total												

 GALDERMA	Title SAP, 43CH1508, Restylane Defyne NLF	Doc id MA-31549
---	--	--------------------

Table 7-5: Optional touch-up treatment eligibility evaluation after initial treatment, FAS

Optional touch-up treatment eligibility	No		Yes		Total (N)	
	n	%	n	%	n	%
Was optimal correction achieved? ¹⁾						
Is the subject unwilling to receive a touch-up?						
Does the subject have any ongoing treatment-related Adverse Events?						
Subject received touch-up treatment						

 $\% = n/N * 100$

1) If optimal correction assessment wasn't performed, note it here.

Table 7-6: Injection method used by treatment visit and treatment, FAS

Injection method	Initial treatment				Optional touch-up treatment			
	Restylane Defyne		Restylane		Restylane Defyne		Restylane	
	n	%	n	%	n	%	n	%
Linear threading								
Other ¹⁾								
Total (N)²⁾								

 $\% = n/N * 100$

1) Specification of Other: ..., ...,

2) A single subject may have been treated by several injection methods.

Table 7-7: Injection depth by treatment visit and treatment, FAS

Injection depth	Initial treatment				Optional touch-up treatment			
	Restylane Defyne		Restylane		Restylane Defyne		Restylane	
	n	%	n	%	n	%	n	%
Middle part of dermis								
Deep layer of dermis								
Other ¹⁾								
Total (N)²⁾								

 $\% = n/N * 100$

1) Specification of Other: ..., ...,

2) A single subject may have been treated at several depths of the skin layer.

 GALDERMA	Title SAP, 43CH1508, Restylane Defyne NLF	Doc id MA-31549
---	--	--------------------

Table 7-8: Topical or local anesthesia used before optional touch-up treatment injection, FAS

Topical or local anesthesia used ¹⁾	Optional touch-up treatment			
	Restylane Defyne		Restylane	
	n	%	n	%
No				
Yes				
Total (N)				

 $\% = n/N * 100$

1) No topical or local anesthesia was used before initial treatment in order to assess pain associated with the injection by VAS.

Table 7-9: Post-treatment care by treatment visit and treatment, FAS

Post-treatment care	Initial treatment				Optional touch-up treatment			
	Restylane Defyne		Restylane		Restylane Defyne		Restylane	
	n	%	n	%	n	%	n	%
None								
Massage								
Ice-pack								
Other ¹⁾								
Total (N)²⁾								

 $\% = n/N * 100$

1) Specification of Other: ..., ...,

2) A single subject may have received several types of post-treatment care.

Table 7-10: Technical problems (device deficiencies) associated with injection by treatment visit and treatment, FAS

Any technical problems (device deficiencies)	Initial treatment ¹⁾				Optional touch-up treatment ²⁾			
	Restylane Defyne		Restylane		Restylane Defyne		Restylane	
	n	%	n	%	n	%	n	%
No								
Yes								
Total (N)								

 $\% = n/N * 100$

1) List technical problems (device deficiencies) for the initial treatment here.

2) List technical problems (device deficiencies) for the touch-up treatment here.

 GALDERMA	Title SAP, 43CH1508, Restylane Defyne NLF	Doc id MA-31549
---	--	--------------------

Table 7-11: Deviations from the treatment procedure as described in the study protocol by treatment visit and treatment, FAS

Any deviations from the treatment procedure	Initial treatment ¹⁾				Optional touch-up treatment ²⁾			
	Restylane Defyne		Restylane		Restylane Defyne		Restylane	
	n	%	n	%	n	%	n	%
No								
Yes								
Total (N)								

% = $n/N * 100$

1) List deviations from the treatment procedure for the initial treatment here.

2) List deviations from the treatment procedure for the touch-up treatment here.

Table 7-12: Directly observed AEs or clinical complications associated with the injection by treatment visit and treatment, FAS

AEs associated with the injection	Initial treatment ¹⁾				Optional touch-up treatment ²⁾			
	Restylane Defyne		Restylane		Restylane Defyne		Restylane	
	n	%	n	%	n	%	n	%
No								
Yes								
Total (N)								

% = $n/N * 100$

1) List directly observed AEs associated with the injection for the initial treatment here.

2) List directly observed AEs associated with the injection for the touch-up treatment here.

8 Appendix E: Efficacy Evaluation

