2.2 Analysis Populations

The following populations will be defined:

- Full Analysis Set (FAS) Includes all subjects who were injected in both NLFs. Subjects are analyzed according to the randomization assignment.
- Per protocol (PP) Includes all FAS subjects who completed the Month 6 follow-up visit without any major deviations.
- Safety Includes all subjects who were injected in at least one NLF, based on the as treated principle.

The FAS population is the primary population for all efficacy analyses. If there are any CSP deviations considered to have substantial impact on the efficacy outcome at the Month 6 follow-up visit, a PP population excluding those subjects will be defined. As this is a non-inferiority trial, non-inferiority will need to be shown in both FAS and PP analyses. Safety analysis will be performed based on the Safety population set.

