2.5 Safety Analysis

All safety variables will be summarized descriptively based on the safety population.

CCI

2.5.2 *Adverse events*

All AEs will be coded according to MedDRA. Treatment emergent adverse events (TEAEs) will be summarized by System Organ Class (SOC) and Preferred Term (PT). The same summaries will be generated for treatment emergent related AEs, severe AEs, AEs leading to discontinuation, and serious AEs (SAEs). An overall summary of number and percentage of subjects with TEAEs reported in total, no TEAEs reported, related and unrelated TEAEs, and the number of events will be compiled (Table 9-5).

For related TEAEs, intensity of the AE will be summarized (Table 9-6). The number of days to onset (Table 9-8) and duration of event (Table 9-7) will be summarized by SOC and PT using number of events, mean, standard deviation, minimum, median, and maximum statistics. Action taken due to a related TEAE will be summarized by SOC, PT, and treatment (Table 9-9) using number of events.

Number and percentage of subjects with unrelated TEAEs and number of events will be presented by SOC, PT and intensity (Table 9-10).

Time to onset of a TEAE will be derived as the start date minus Day 1. If the start date is missing, it will be assumed that the AE started on Day 1.

Duration of a TEAE will be derived as the stop date minus the start date +1. If the start date is missing, it will be assumed that the AE started on Day 1. Missing stop date will not be imputed and therefore no duration will be calculated in these cases. Instead, the number of TEAEs that were ongoing at the end of the study will be given.

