9.3.2 Related TEAEs

Table 9-6: Related TEAEs by MedDRA System Organ Class, Preferred Term, and intensity, Safety population

Primary System Organ Class Preferred Term	Restylane Defyne									Restylane									Total					
	Events	Subjects	Intensity						Events	Subjects	Intensity						Events	Subjects						
			Mild		Moderate		Severe				Mild		Moderate		Severe									
	n	n	%	n	%	n	%	n	%	n	n	%	n	%	n	%	n	n	%	n	%			
SOC																								
PT																								
PT																								
...																								
SOC																								
PT																								
PT																								
...																								
All¹⁾																								

% = n / number of subjects in Safety population (N = xxx) * 100

1) A single subject may have reported several related TEAEs.

 GALDERMA	Title SAP, 43CH1508, Restylane Defyne NLF	Doc id MA-31549
--	--	--------------------

Table 9-7: Duration (number of days days) of related TEAEs by MedDRA System Organ Class and Preferred Term, Safety population

Primary System Organ Class Preferred Term	Restylane Defyne						Restylane					
	Events n	Mean	SD	Min	Median	Max	n	Mean	SD	Min	Median	Max
SOC												
PT												
PT												
...												
SOC												
PT												
PT												
...												
All												

If applicable, list TEAEs ongoing at study end here, alternatively create a summary table.

 GALDERMA	Title SAP, 43CH1508, Restylane Defyne NLF	Doc id MA-31549
--	--	--------------------

Table 9-8: Time to onset (number of days) from treatment for related TEAEs by MedDRA System Organ Class and Preferred Term, Safety population

Primary System Organ Class Preferred Term	Restylane Defyne						Restylane					
	Events n	Mean	SD	Min	Median	Max	n	Mean	SD	Min	Median	Max
SOC												
PT												
PT												
...												
SOC												
PT												
PT												
...												
All												

Any extra comments here...

 GALDERMA	Title SAP, 43CH1508, Restylane Defyne NLF	Doc id MA-31549
--	--	--------------------

Table 9-9: Action taken due to related TEAEs by MedDRA System Organ Class and Preferred Term, Safety population

Primary System Organ Class Preferred Term	Action Taken							
	Restylane Defyne				Restylane			
	None	Medication treatment	Non-pharmacological treatment or other procedures/tests	Subject withdrawn	None	Medication treatment	Non-pharmacological treatment or other procedures/tests	Subject withdrawn
SOC								

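### SAP Tables 7-10 and 7-12 put device deficiencies and directly observed injection AEs on the FAS, against the SAP's own Safety-population rule

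*SAP*

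**What the plan says.** SAP Section 2.2 defines two populations that matter here.

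- FAS: "Includes all subjects who were injected in both NLFs. Subjects are analyzed according to the randomization assignment".
- Safety: "Includes all subjects who were injected in at least one NLF, based on the as treated principle".

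The same section adds "Safety analysis will be performed based on the Safety population set", and protocol Section 10.2 gives the same rule. SAP Section 2.5 is broader: "All safety variables will be summarized descriptively based on the safety population". SAP Section 1.5 (Safety Assessments) lists adverse events and device deficiency among the safety data.

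Two table shells in SAP Appendix D carry a different label. Table 7-10 is titled "Technical problems (device deficiencies) associated with injection by treatment visit and treatment, FAS" and Table 7-12 is titled "Directly observed AEs or clinical complications associated with the injection by treatment visit and treatment, FAS". In both, footnotes are reserved for listing the individual problems or events.

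The tables are called from SAP Section 2.3.5 (Extent of exposure), which names no population. Section 2.3.4, just before it, does state that its own summaries use the FAS. The legible part of SAP Section 2.8 (changes from the protocol) mentions no exception for these two tables.

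**The concern.** The two populations differ in exactly two ways, and both bear on what these tables are meant to show.

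First, the FAS leaves out anyone injected in only one fold. Protocol Section 4.4.1 always starts with the right fold. A subject whose initial treatment ends after that fold, whatever the reason, is in the Safety population but not in the FAS. If the reason was an injection complication or a device problem, the event is missing from the table built to report it, and from the footnote listing. That is selection on the outcome being tabulated.

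Second, the FAS assigns events by randomised product. SAP Table 2-1 foresees products given on the wrong sides, and the same product given in both folds. In either case an event on the misassigned fold would appear under a product that fold never received.

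The trial is meant to support registration of a device (protocol Section 2.5), so counts of device deficiencies and injection complications by product should be right even when they are small.

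**Working it through.** There is no stated figure to reproduce: the sample-size sections are redacted, and the point does not depend on power or alpha. The main check is to set the rules side by side.

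| Item | Safety data under SAP 1.5? | Rule in SAP 2.2 and 2.5 | Label on the shell |
|---|---|---|---|
| Device deficiencies (Table 7-10) | Yes | Safety, as treated | FAS |
| Directly observed injection AEs (Table 7-12) | Yes | Safety, as treated | FAS |
| TEAEs (Tables 9-5 to 9-9) | Yes | Safety, as treated | Safety |

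On the legible text, the SAP therefore puts AE tables on two different populations without saying why.

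**Single-fold subjects.** Inputs: N = 175 planned subjects (SAP Section 1.1.2), and k subjects stopped after the first fold at initial treatment. The documents give no value for k, so it is an assumption. Suppose each of the k subjects has an event and nobody else does. The FAS shows 0/(175 − k). The Safety population shows k/175, counting all Safety subjects.

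| k | FAS | Safety |
|---|---|---|
| 0 | 0/175 | 0/175 |
| 1 | 0/174 = 0.00% | 1/175 = 0.57% |
| 2 | 0/173 = 0.00% | 2/175 = 1.14% |
| 3 | 0/172 = 0.00% | 3/175 = 1.71% |

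If five other subjects also have an event, k = 1 gives 5/174 = 2.87% against 6/175 = 3.43%, and k = 2 gives 5/173 = 2.89% against 7/175 = 4.00%.

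**How likely is k ≥ 1?** Let p be the risk that initial treatment stops after one fold. The expected number is 175p, and the chance of at least one is 1 − (1 − p)^175. The range for p is again an assumption.

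- p = 0.2%: expected 0.35, chance 1 − 0.998^175 = 30%.
- p = 0.5%: expected 0.875, chance 58%.
- p = 1%: expected 1.75, chance 83%.
- p = 2%: expected 3.5, chance 97%.

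**Product errors.** Take one subject with products swapped between sides and an event only on the fold actually injected with Restylane Defyne. The FAS rule gives Defyne 0 and Restylane 1; as treated, it is Defyne 1 and Restylane 0. Each such subject moves one event to the other column.

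**Limit.** The single-fold exclusion arises only at the initial treatment. A subject stopped after one fold at touch-up has already had both folds injected and stays in the FAS. Product errors can matter at either visit.

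**The case against.** The strongest reply is that these are exposure tables, not the safety analysis. They are called from Section 2.3.5 and sit in an appendix labelled FAS throughout. The main AE analysis is intact: protocol Section 8.4.4 sends every AE to the eCRF, and Tables 9-5 to 9-9 use the Safety population. A reader might infer from the FAS label that injection AEs are lost from the report or biased downward in it. The documents do not support that. For AEs, the harm is that Table 7-12 may disagree with Appendix F.

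A reader might also infer that device deficiencies are summarised nowhere else. That cannot be shown. The pages of Appendix F before Section 9.3, part of SAP Section 2.5 and part of the safety endpoints are redacted, so a Safety-population table may exist there. Each deficiency is also recorded on a complaint form and assessed by the investigator and the sponsor (protocol Sections 8.5.2 and 8.5.3), whatever the analysis set.

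The route from a technical failure to an untreated second fold is uncertain too. Two needles come with each syringe, and protocol Section 6.6.1 describes repositioning or checking the needle when resistance is met. Nothing in the documents says that a deficiency ends the session. In the earlier 162-subject US split-face study, as described in protocol Section 2.4.2, the two discontinuations for product-related AEs concerned both sides of the face, and no single-fold stop is mentioned.

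What stands is that the number of subjects is likely to be very small and that the AE data survive elsewhere. What does not stand is the exposure label as an excuse: Section 1.5 classes both items as safety data, Section 2.5 covers all safety variables, and no exception is written.

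**Conclusion.** The labels on Tables 7-10 and 7-12 contradict the SAP's own rule. Followed as written, they would omit a subject stopped after the first fold at initial treatment and would credit an event after a product error to the randomised product. This is a small consistency correction with no bearing on the primary analysis.

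Its size depends on counts that the documents do not give. With no single-fold subjects and no product errors, the FAS and Safety versions are identical. A reader might infer that a large share of complications would go missing, but no such share can be supported: one or two omitted out of five events would be 20% to 40%, and one or two out of fifty would be 2% to 4%. Both totals are arbitrary, and protocol Sections 2.7 and 8.4.8 describe injection reactions as common.

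The same argument might seem to reach Tables 7-11 and 9-6. It does not. Table 7-11 lists deviations from the treatment procedure, which Section 1.5 does not class as safety data. Table 9-6 already uses the Safety population. Its percentages ("n / number of subjects in Safety population (N = xxx) * 100") include any subject who never received the product in question, but three such subjects would be 3/175 = 1.7% of the denominator. The table has no visit dimension on which a per-visit count could be based.

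**What to change.** Retitle Tables 7-10 and 7-12 from FAS to Safety population, with columns by product actually injected. Both shells already have a Total (N) row for each product and visit; let it count the subjects injected with that product at that visit. The footnote listings should cover the same subjects. If the FAS was intended, SAP Section 2.3.5 should state and justify the exception.

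The cost is a population label and a filter in two table programs. The small downside is that these two tables would no longer share denominators with the other Appendix D tables, which a footnote can explain. Tables 7-11 and 9-6 need no change on this ground.
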